8.2.8 Injection site reaction assessments

Based on the SC mode of administration of high doses of protein and on a higher incidence of local injection site reactions observed at the highest dose level (300 mg weekly) in dupilumab studies, severe injection site reactions are considered a potential risk. Participants who experience an injection site reaction must be closely monitored for the possibility of a more intense injection site reaction with a future injection. Any severe injection reaction that lasts over 24 hours will be reported as an AESI ([Section 8.3.6](#)) with immediate notification.

Prophylactic treatment/premedication for an injection site reaction is not permitted.

8.3 ADVERSE EVENTS, SERIOUS ADVERSE EVENTS AND OTHER SAFETY REPORTING

The definitions of AEs and SAEs can be found in Appendix 3 ([Section 10.3](#)). The definition of AESI is provided in [Section 8.3.6](#).

The definitions of unsolicited and solicited AEs can be found in Appendix 3 ([Section 10.3](#)).

Adverse events will be reported by the participant (or, when appropriate, by a caregiver, surrogate, or the participant's LAR).

The Investigator and any qualified designees are responsible for detecting, documenting, and recording events that meet the definition of an AE or SAE and remain responsible for following up all AEs that are considered related to the study intervention or study procedures or that cause the participant to discontinue the study intervention (see [Section 7](#)).

The method of recording, evaluating, and assessing the causality of AEs and SAEs and the procedures for completing and transmitting SAE reports are provided in Appendix 3 ([Section 10.3](#)).

8.3.1 Time period and frequency for collecting AE and SAE information

All AEs (serious or nonserious) will be collected from the signing of the ICF until the EOT/EOS Visit at the time points specified in the SoA ([Section 1.3](#)).

All SAEs and AESI will be recorded and reported to the Sponsor or designee immediately, and under no circumstance should this exceed 24 hours, as indicated in Appendix 3 ([Section 10.3](#)). The Investigator will submit any updated SAE data to the Sponsor within 24 hours of the data being available.

The Investigator should take appropriate measures to follow all AEs until clinical recovery is complete and laboratory results have returned to normal, until progression has been stabilized, or until death, in order to ensure the safety of the participants. This may imply that observations will continue beyond the last planned visit per protocol and that additional investigations may be requested by the monitoring team up to the time as noticed by the Sponsor.

The Investigators are not obligated to actively seek information on AEs or SAEs after conclusion of the study participation. However, if the Investigator learns of any SAE, including a death, at any time after a participant has been discharged from the study and he/she considers the event to be reasonably related to the study intervention or study participation, the Investigator must promptly notify the Sponsor.

8.3.2 Method of detecting AEs and SAEs

Care will be taken not to introduce bias when detecting AEs and/or SAEs. Open-ended and non-leading verbal questioning of the participant is the preferred method to inquire about AE occurrences.

8.3.3 Follow-up of AEs and SAEs

After the initial AE/AESI/SAE report, the Investigator is required to proactively follow each participant at subsequent visits/contacts. At the prespecified study end-date, all SAEs and AESIs (as defined in [Section 8.3.6](#)) will be followed until resolution, stabilization, the event is otherwise explained, or the participant is lost to follow-up (as defined in [Section 7.3](#)). Further information on follow-up procedures is provided in Appendix 3 ([Section 10.3](#)).

8.3.4 Regulatory reporting requirements for SAEs

- Prompt notification by the Investigator to the Sponsor of an SAE is essential so that legal obligations and ethical responsibilities towards the safety of participants and the safety of a study intervention under clinical investigation are met.
- The Sponsor has a legal responsibility to notify both the local regulatory authority and other regulatory agencies about the safety of a study intervention under clinical investigation. The Sponsor will comply with country-specific regulatory requirements relating to safety reporting to the regulatory authority, Institutional Review Boards (IRBs), and the Investigators.

- Serious adverse events that are considered expected will be specified in the Package Insert.
- Investigator safety reports must be prepared for suspected unexpected serious adverse reactions (SUSARs) according to local regulatory requirements and Sponsor policy and forwarded to Investigators as necessary.
- An Investigator who receives an investigator safety report describing an SAE, SUSAR, or any other specific safety information (eg, summary or listing of SAEs) from the Sponsor will review and then file it along with Package Insert and will notify the IRB, if appropriate according to local requirements. It is the responsibility of the Sponsor to assess whether an event meets the criteria for a SUSAR and, therefore, is expedited to regulatory authorities.

8.3.5 Pregnancy

- Details of all pregnancies in female participants and female partners of male participants will be collected after the start of study intervention and until EOT/EOS.
- If a pregnancy is reported, the Investigator will record pregnancy information on the appropriate form and submit it to the Sponsor within 24 hours of learning of the female participant's pregnancy and should follow the procedures outlined in Appendix 4 ([Section 10.4](#)).
- Abnormal pregnancy outcomes (eg, spontaneous abortion, fetal death, stillbirth, congenital anomalies, ectopic pregnancy) are considered SAEs and will be reported as such.
- The participant or pregnant female partner will be followed to determine the outcome of the pregnancy. The Investigator will collect follow-up information on the participant or pregnant female partner and the neonate, and the information will be forwarded to the Sponsor.
- Any post-study pregnancy-related SAE considered reasonably related to the study intervention by the Investigator will be reported to the Sponsor as described in [Section 10.3.4](#). While the Investigator is not obligated to actively seek this information in former study participants or pregnant female partners, he/she may learn of an SAE through spontaneous reporting.
- Any female participant who becomes pregnant while participating in the study will discontinue the study intervention.

8.3.6 Adverse event of special interest

An AESI is an AE (serious or nonserious) of scientific and medical concern specific to the Sponsor's product or program, for which ongoing monitoring and immediate notification by the Investigator to the Sponsor are required. Such events may require further investigation in order to characterize and understand them. Adverse events of special interest may be added, modified, or removed during a study by protocol amendment.

For these AESIs, the Sponsor will be informed immediately (ie, within 24 hours), per the SAE notification described in [Section 10.3.4](#), even if it does not fulfill a seriousness criterion.

Adverse event of special interests for this study include the following:

- Anaphylactic or systemic allergic reactions that are related to IMP and that require treatment (refer to Appendix 12 [[Section 10.12](#)] for the definition of anaphylaxis)
 - Severe injection site reactions that last longer than 24 hours
 - Conjunctivitis, blepharitis, or keratitis
 - Serum sickness or serum sickness-like reaction
 - Clinically symptomatic eosinophilia (or eosinophilia associated with clinical symptoms)
 - Any infection meeting at least 1 of the following criteria:
 - Any SAE of serious infection
 - Requires parenteral (intravenous, intramuscular, SC) antimicrobial therapy
 - Requires oral antimicrobial therapy for longer than 2 weeks
 - Is a parasitic infection
 - Is an opportunistic infection (refer to Appendix 9 [[Section 10.9](#)])
- Note:** Antimicrobial therapy refers to antibiotic, antiviral, and antifungal agents.
- Significant elevation of alanine aminotransferase (ALT)
 - $ALT > 5 \times ULN$ in participants with baseline $ALT \leq 2 \times ULN$
 - or
 - $ALT > 8 \times ULN$ if baseline $ALT > 2 \times ULN$
 - Pregnancy of a female participant as well as pregnancy occurring in a female partner of a male participant entered in a study with IMP
 - Pregnancy occurring in a female participant entered in the clinical study or in a female partner of a male participant entered in the clinical study. It will be qualified as an SAE only if it fulfills one of the seriousness criteria (see Appendix 3 [[Section 10.3](#)]).
 - In the event of pregnancy in a female participant, IMP should be discontinued.
 - Follow-up of the pregnancy in a female participant or in a female partner of a male participant is mandatory until the outcome has been determined (See Appendix 4 [[Section 10.4](#)]).
 - Symptomatic overdose (serious or nonserious) with IMP
 - An overdose (accidental or intentional) with the IMP is an event suspected by the Investigator or spontaneously notified by the participant and defined as at least twice the intended dose during an interval of less than 11 days. The circumstances (ie, accidental or intentional) should be clearly specified in the verbatim and symptoms, if any, entered on separate AE forms.

Of note, asymptomatic overdose has to be reported as a standard AE.

8.3.7 Guidelines for management of specific laboratory abnormalities

Decision trees for the management of certain laboratory abnormalities by Sanofi are provided in Appendix 5 ([Section 10.5](#)).

The following laboratory abnormalities should be monitored, documented, and managed according to the related flow chart in protocol appendices.

- Neutropenia
- Thrombocytopenia
- Increase in ALT
- Increase in serum creatinine
- Increase in creatine phosphokinase (CPK)

8.3.8 Guidelines for reporting product complaints

Any defect in the IMP must be reported as soon as possible by the Investigator to the monitoring team, which will complete a product complaint form within the required timelines.

Appropriate information (eg, samples, labels or documents like pictures, or photocopies) related to product identification and to the potential deficiencies may need to be gathered. The Investigator will assess whether or not the quality issue has to be reported together with an AE or SAE.

8.4 PHARMACOKINETICS

Pharmacokinetics parameters are not evaluated in this study.

8.5 GENETICS

Genetics are not evaluated in this study.

8.6 BIOMARKERS

Biomarkers are not evaluated in this study.

8.7 IMMUNOGENICITY ASSESSMENTS

Immunogenicity is not evaluated in this study.

8.8 HEALTH ECONOMICS OR MEDICAL RESOURCE UTILIZATION AND HEALTH ECONOMICS

Health economics or medical resource utilization and health economics parameters are not evaluated in this study.

8.9 USE OF DATA FOR FUTURE RESEARCH

Not applicable.

9 STATISTICAL CONSIDERATIONS

This postmarketing study is to assess whether dupilumab used without INCS will show similar efficacy to that of dupilumab used with INCS in EFC14280, using the point estimates of the proportion of responders (NPS improvement from baseline ≥ 1) at Week 24. Formal statistical analysis for hypothesis (null/alternative) will not be performed.

9.1 SAMPLE SIZE DETERMINATION

In EFC14280, the proportion of responders (NPS improvement from baseline ≥ 1) at Week 24 was 62.0% in the dupilumab group. Based on this result, the proportion of responders (NPS improvement from baseline ≥ 1) at Week 24 in this postmarketing study will be at least 50.0% to justify the similar effect size between EFC14280 and this study.

It is necessary for 20 participants to achieve this similar responder rate (at least 50%) with a 90% probability of success. The sample size was adjusted up to 25 to account for a 20% drop-out rate.

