## 2 SAMPLE SIZE DETERMINATION

The EFC14280 study, which was conducted as a pivotal study for Nasal Polyposis, the proportion of responders (NPS improvement from baseline  $\geq 1$ ) at Week 24 was 62.0% in the dupilumab group. Based on this result, the target proportion of responders (NPS improvement from baseline  $\geq 1$ ) at Week 24 in this postmarketing study is at least 50.0% to reflect the similar effect size between EFC14280 and this study.

It is necessary for 20 participants to achieve this response rate (at least 50%) with a 90% probability of success. The sample size was adjusted up to 25 to account for a 20% drop-out rate.

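### An observed responder rate of 50% or more is taken to show an effect similar to 62%, but a true rate of 40% would also meet that rule 15% to 24% of the time, and the plan states only the 90% chance of passing

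*Protocol*

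**What the plan says.** Protocol section 9 asks whether dupilumab without intranasal corticosteroid is similar in efficacy to dupilumab with it in EFC14280, "using the point estimates of the proportion of responders". It adds: "Formal statistical analysis for hypothesis (null/alternative) will not be performed".

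Section 9.1 gives the reference rate ("at Week 24 was 62.0% in the dupilumab group") and says that the rate in this study "will be at least 50.0% to justify the similar effect size between EFC14280 and this study". SAP section 2 words this more softly, as a target rate that "is at least 50.0% to reflect the similar effect size between EFC14280 and this study".

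On size, section 9.1 states: "It is necessary for 20 participants to achieve this similar responder rate (at least 50%) with a 90% probability of success". It continues: "The sample size was adjusted up to 25 to account for a 20% drop-out rate".

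The responder percentage is reported with a 95% confidence interval in the per protocol (PP) set (Protocol 9.3.2); the SAP makes this a continuity-corrected Wilson interval (4.3.2). Neither document gives the interval a role in the similarity conclusion. Neither states a margin, an unacceptable rate, or the probability of meeting the target when the true rate is below 62%.

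**The concern.** The plan attaches an inference, similarity to a 62% rate, to a threshold on a bare point estimate in a small single-arm study. A reader sees the 90% and has nothing to set beside it. How often would a clearly lower true rate also reach 50%, and how much does a result just at 50% say about the true rate?

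This bears on the study's main purpose. Protocol 2.1 says that approval in Japan was conditional on assessing monotherapy after approval, and that the pivotal Phase 3 studies collected no monotherapy data. There is no concurrent control, so for the primary endpoint the comparison with the EFC14280 rate carries the similarity claim.

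**Working it through.** **Inputs.** Reference rate 62.0%, threshold at least 50.0%, 20 participants, 90% probability of success, 20% dropout and 25 enrolled (Protocol 9.1). PP set: dosed participants who received no intranasal corticosteroid up to Week 24 (Protocol 9.2). Missing Week 24 data count as nonresponse (Protocol 9.3.2). The true rates of 40% and 30% are illustrative and are not in the documents; 50% is the plan's own target.

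**The plan's figures.** The documents do not name the true rate behind the 90%; 62% is inferred. With at least 10 responders of 20, the exact binomial tail is P(X ≥ 10 | n = 20, p = 0.62) = 0.908, which agrees with 90%. Other readings fit less well: more than 50% (at least 11 of 20) gives 0.810, and a normal approximation without continuity correction gives 0.866. Enrolment: 20 / (1 − 0.20) = 25, as stated.

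**Which denominator.** Twenty is the number left after dropout. The PP definition does not remove dropouts; it removes only undosed participants and users of intranasal corticosteroid. A dropout with no Week 24 score stays in as a nonresponder. The analysed number is therefore likely to be nearer 25, where 50% means at least 12.5, that is 13 responders.

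**Pass probabilities.** For a true rate p these are P(X ≥ 10 | 20, p) and P(X ≥ 13 | 25, p). The last column covers the case where 62% is a rate among observed participants and 20% drop out independently of response; the effective rate is then 0.8p, for example 0.8 × 0.62 = 0.496.

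| True rate p | ≥10 of 20 | ≥13 of 25 | ≥13 of 25, 20% counted as nonresponders |
|---|---|---|---|
| 62% | 0.91 | 0.89 | 0.48 |
| 50% | 0.59 | 0.50 | 0.15 |
| 40% | 0.24 | 0.15 | 0.03 |
| 30% | 0.05 | 0.02 | 0.002 |

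**What a just-passing result shows.** The lower limit of the continuity-corrected Wilson interval is [2np̂ + z² − 1 − z√(z² − 2 − 1/n + 4p̂(n(1 − p̂) + 1))] / [2(n + z²)], with z = 1.96 and z² = 3.84.

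- 10/20: (20 + 3.84 − 1 − 1.96 × √23.79) / 47.68 = 0.279. By symmetry the upper limit is 0.721.
- 13/25: the same formula gives 0.318, and its upper-limit counterpart gives 0.717.

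Both intervals contain 62% and 40%.

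**The case against.** The strongest reply is that the plan is openly descriptive. It tests no hypothesis, so no error rate has been promised and none is breached. That stands: the figures above describe how a descriptive criterion behaves. It does not rescue the wording, because saying that a point estimate justifies a similar effect size is itself an inference.

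Three stronger readings are tempting, and the documents do not support them.

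- A reader might infer that passing 59% of the time at a true 50% is a false pass. Under the plan's own target a true 50% counts as similar, so it is an error only if one rejects that limit. The documents give no justification for the limit, but they do not contradict it either. The 40% case is the clearer one.
- A reader might take the figures for 20 as those of the planned analysis and call the rule lenient. The PP set and the nonresponder rule point nearer to 25, where the probabilities at 50% and 40% are lower. If 62% excludes missing data and 20% drop out, the rule is strict, and the stated 90% becomes about 48%.
- A reader might infer that similarity rests on this one figure. It does not. The interval will be reported, a modified intent-to-treat analysis is planned (SAP 4.3.4), and Protocol 3.1 and 4.2.2 say that the changes in nasal polyp, congestion and Lund Mackay scores will also be evaluated to show similar efficacy. None of these, however, alters the criterion in section 9.1.

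**Conclusion.** The concern holds in a limited form. Meeting 50% does not by itself establish similarity to 62%: a true rate of 40% meets it with probability 0.24 (n = 20) or 0.15 (n = 25), and a just-passing result leaves an interval of roughly 28–72% or 32–72%. The plan gives the favourable operating characteristic and omits the others.

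These sizes assume independent binomial responses and either 20 or 25 analysed participants. They also assume that 62% is the rate behind the 90% and already counts missing data as nonresponse, or that no data are missing. The documents do not settle that last assumption, and the results depend on it heavily.

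The figure at 30% needs care. It is the probability of passing if the true rate were 30%, about 5% at n = 20 or 2% at n = 25. It is not the probability that the true rate is that low once the rule has been met.

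**What to change.** Keep the sample size and the 50% target. In Protocol 9 and 9.1 and SAP 2:

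1. Present 50% as a descriptive target for the observed rate, and drop the statement that reaching it justifies or reflects a similar effect size.
2. Require the conclusion on the primary endpoint to rest on the point estimate together with the planned 95% confidence interval, with no claim of similarity from the point estimate alone.
3. Beside the 90%, state the pass probabilities at true rates of 62, 50, 40 and 30%: 0.91, 0.59, 0.24 and 0.05 for 20 analysed, and 0.89, 0.50, 0.15 and 0.02 for 25.
4. Say whether the assumed 62% already counts missing data as nonresponse. If it does not, add the figures for 20% dropout independent of response: about 0.48, 0.15, 0.03 and 0.002.
5. Word the low-rate property conditionally: if the true rate were 30%, the rule would be met about 5% of the time with 20 analysed, or 2% with 25.

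The change needs no further participants, assessments or analyses. Its cost is wording and a less favourable claim.

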9.2 POPULATIONS FOR ANALYSES

The populations for analyses are defined in [Table 5](#).

Table 5 - Populations for analyses

Population	Description
Screened	All participants who sign the informed consent form (ICF)
Enrolled	The enrolled population includes all participants with a treatment kit number allocated and recorded in the interactive response technology (IRT) database, regardless of whether the treatment kit was used or not. Participants treated without a treatment kit number being allocated will not be considered enrolled and will not be included in any efficacy population.
Intent-to-treat (ITT)	Enrolled population with chronic rhinosinusitis with nasal polyp (CRSwNP)
Modified intent-to-treat (mITT)	All participants in ITT allocated to study intervention administered at least 1 dose of study intervention
Per protocol (PP)	All participants in mITT allocated to study intervention administered at least 1 dose of study intervention, and who did not receive intranasal corticosteroids (INCS) up to Week 24
Per protocol with extension term (PPE)	All participants in mITT allocated to study intervention administered at least 1 dose of study intervention during the intervention period after Week 24, and who did not receive INCS throughout the study
Safety (SAF)	All participants allocated to study intervention administered at least 1 dose of study intervention before Week 24
Safety for extension term (SAFE)	All participants allocated to study intervention administered at least 1 dose of study intervention during the intervention period after Week 24

Abbreviations: CRSwNP: chronic rhinosinusitis with nasal polyp; ICF: informed consent form; INCS: intranasal corticosteroids; IRT: interactive response technology; ITT: intent-to-treat; mITT: modified ITT; PP: per protocol; PPE: per protocol with extension term; SAF: safety; SAFE: safety for extension term

Efficacy analyses for the treatment period up to Week 24 will be performed using the per protocol (PP) population. Efficacy analyses for the treatment period after Week 24 will be performed using the per protocol with extension term (PPE) population. Additionally, supportive efficacy analyses will be performed using the modified intent-to-treat (mITT) population.

Safety data up to Week 24 will be reported for the safety (SAF) population. Safety data collected after Week 24 will be reported for the safety for extension term (SAFE) population.

Participants exposed to study intervention before or without being enrolled will not be considered enrolled and will not be included in any efficacy or safety populations. The safety experience of these participants will be reported separately.

Enrolled participants for whom it is unclear whether they took the study intervention will be considered as exposed and will be included in the safety populations.

For any participant enrolled more than once, only the data associated with the first enrollment will be used in any efficacy or safety population. The safety experience associated with any later enrollment will be reported separately.

9.3 STATISTICAL ANALYSES

The statistical analysis plan (SAP) will be finalized prior to database lock and will include a more technical and detailed description of the statistical analyses described in this section. This section is a summary of the planned statistical analyses of the most important endpoints including primary and key secondary endpoints.

A primary database lock will be performed when all participants have completed their treatment phase. Final analyses in the clinical study report will be based on all data collected up to this database lock.

